
The primary endpoint in this study is RSV RNA \log_{10} viral load (measured by qRT-PCR assay in the mid-turbinate nasal swab specimens) AUC immediately prior to first dose of study drug (baseline) over 7 days. Mean \log_{10} viral load values over time will be analyzed using a restricted maximum likelihood-based repeated measures approach. Analyses will include the fixed, categorical effects of treatment, strata, visit, and treatment-by-visit interaction, as well as the continuous, fixed covariates of baseline \log_{10} viral load and baseline \log_{10} viral load by visit interaction. An unstructured (co)variance structure will be used to model the within subject errors over time. The Kenward Roger method will be used to approximate the degrees of freedom. The difference in the AUCs for active versus placebo will be derived using appropriate contrasts deriving least square mean differences, including the 95% 2-sided confidence intervals. For inferential purposes, p-values will be compared with significance levels controlling for the (family-wise) type 1 error rate.

For differences between treatment groups on qRT-PCR, the same methods as for the primary endpoint will be used, using appropriate contrasts to estimate treatment differences between the various treatment groups by treatment day using nominal 95% confidence intervals. The time to virus not detected is defined as the time from initiation of study treatment until the time at which it is observed that the virus is undetectable in an assessment and after which time no virus positive assessment follows. The time to clinical stability is defined as the time from initiation of study treatment until the time at which the

following criteria are met: return to pre-RSV infection status (hereafter referred to as “normalization”) of blood oxygen level (ie, no additional requirement of supplemental oxygen compared with pre-RSV infection status), normalization of oral feeding, normalization of respiratory rate, and normalization of heart rate. Additionally, statistical modeling will be performed on the secondary endpoint of length of hospital stay, defined as the time from treatment initiation to hospital discharge in hours. Parent/caregiver-reported and clinician-reported eCOA (PRESORS) will be descriptively summarized by treatment group and compared across treatment groups.

Population PK analysis of concentration-time data of JNJ-63549109 will be performed using nonlinear mixed-effects modeling. Subjects will be excluded from the PK analysis if their data do not allow for accurate assessment of the PK.

Statistical approaches to explore correlations between clinical outcome and biomarkers vary and depend on the different data types of the applied technology platforms, as well as on the extent of observed differences among study subjects. Analyses may be conducted at the sponsor’s discretion and reported separately from this study. Selected efficacy and safety parameters will be subject to PK/PD analysis. JNJ-63549109 exposures will be evaluated as an independent variable, with selected efficacy and selected safety parameters considered as dependent variables. Various approaches, including graphical analysis, linear, nonlinear, and logistic regression methods may be utilized.

Medical resource utilization and health economics will be descriptively summarized by treatment regimen and compared across treatment regimens.

Safety data will be presented descriptively. No statistical testing of safety data is planned. For safety, baseline is defined as the last assessment prior to the first intake of study drug.

TIME AND EVENTS SCHEDULE: DURING HOSPITALIZATION (UP TO DISCHARGE)

Phase	Screening	Treatment Phase			Follow-up Phase ^a						
Day	0	1	2	3 to 6 ^b	7 ^c (+2 days)	8 to 9	10 (+2days)	11 to 13	14 (+2 days)	15 to 27	28 (±2 days) EoS
Study Procedure ^d											
Screening/Administrative											
Informed consent form	X										
Demographics	X										
Medical history	X										
Inclusion/exclusion criteria ^e	X										
Body weight	X				X		X		X		X
Body length and head circumference	X										X
Study Drug Administration ^f											
Randomization		X									
Dispense/administer study drug ^g		X	X	X							
Clinical Efficacy Evaluations											
Parent(s)/caregiver(s) eCOA ^h	X	bid ^{i,j}	bid ⁱ	bid	bid	bid	bid	bid	bid	bid	bid
Clinical evaluation ^k	X	bid	bid	bid	bid	bid	bid	bid	bid	bid	bid
Clinician eCOA	X	bid	bid	bid	bid	bid	bid	bid	bid	bid	bid
Oxygen saturation (SpO ₂) ^l	X (Q4h)	X (Q4h)	X (Q4h)	X (Q4h)	X (Q4h)	X (Q8h)	X (Q8h)	X (Q8h)	X (Q8h)	X (Q8h)	X (Q8h)
Medical resource utilization and health economics assessment	X	X	X	X	X	X	X	X	X	X	X
Clinical Safety Evaluations											
Complete physical examination ^m	X										X
Directed physical examination ⁿ		X	X		X		X		X		
Electrocardiogram ^o	X			X ^p							X
Vital signs	X	bid	bid	bid	bid	bid	bid	bid	bid	bid	bid

Phase Day	Screening 0	Treatment Phase			Follow-up Phase ^a							
		1	2	3 to 6 ^b	7 ^c (+2 days)	8 to 9	10 (+2days)	11 to 13	14 (+2 days)	15 to 27	28 (±2 days) EoS	
Study Procedure^d												
Nasal Swabs ^q												
Mid-turbinate nasal swab (if non-intubated) or endotracheal sample (if intubated): RSV diagnosis confirmation, viral and bacterial coinfection ^r	X											
Mid-turbinate nasal swab (if non-intubated) or mid-turbinate nasal swab and endotracheal sample (if intubated): RSV viral load, viral resistance (genome sequencing), biomarker, and infectious RSV viral load (plaque assay) ^s		X ^t	X	X	X		X		X			X
Clinical Laboratory Assessments												
Blood sampling for hematology ^u	X		X		X				X			
Blood sampling for biochemistry ^u	X				X				X			X
Urinalysis ^v	X			X					X			
Pharmacokinetics ^q												
Blood sampling for pharmacokinetics	Day 1 to Day 2											
		Post Dose 1	Post Dose 2									
		0.25 - 2h	0.5 - 1h 7h (±4)									
Group X ^w :		X	(X) ^x		X							
Group Y ^w :		X		(X) ^x	X							
Ongoing Subject Review												
Prior and Concomitant therapy	X	X	X	X	X	X	X	X	X	X	X	X
Adverse events	X	X	X	X	X	X	X	X	X	X	X	X

Abbreviations: bid: twice daily; ECG: electrocardiogram; eCOA: electronic clinical outcome assessment; eCRF: electronic case report form; EoS: end of study; IDMC: Independent Data Monitoring Committee; LD: loading dose; MD: maintenance dose; PK: pharmacokinetic(s); Q4h: every 4 hours; Q8h: every 8 hours; RSV: respiratory syncytial virus; SpO₂: peripheral capillary oxygen saturation.

Footnotes:

- a. If a subject is discontinued from study drug, a follow-up visit will be scheduled 2 days (+2 days), 5 days (+2 days), 9 days (+2 days), and 23 days (± 2 days) after the last dose of study drug was administered. Assessments should be performed as indicated in the Time and Events Schedule, respectively for the Day 7, Day 10, Day 14, and Day 28 visit.
- b. The subject may be discharged after Day 2 study procedures, but may also remain hospitalized if deemed appropriate by the investigator. Hospitalization duration will not be extended solely for study purposes.
- c. If treatment duration is increased to up to 10 days, then all assessments performed on Day 7 will again be performed 1 day (+2 days) after administration of the last MD.
- d. The results of clinical/safety evaluations that are performed as part of routine clinical care while hospitalized will be collected in the eCRF for viral, safety, and/or clinical evaluation.
- e. Procedures performed as part of standard of care within approximately 72 hours prior to screening completion (ie, randomization) may be used in determining study eligibility.
- f. One LD followed by 9 MDs twice daily. MDs may be extended to up to 19 doses over 10 days if recommended by the IDMC.
- g. Study drug LD should be given as soon as possible but no later than 4 hours after randomization. Subjects will be dosed with a single LD followed by 9 MDs twice daily (minimum 8 hours and maximum 16 hours apart with no more than 2 doses per calendar day) from Day 1 to Day 5/6 (depending on the timing of the LD). Lumicitabine may be given without regard to food. The date and time of dose administration, the date and time of food intake (limited to the food ingested within 30 minutes before or after study drug administration), and the type of food will be recorded in the eCRF.
- h. An electronic device will be provided to the parent(s)/caregiver(s) at screening and the investigator/study-site personnel will provide sufficient information to enable the parent(s)/caregiver(s) to complete the parent(s)/caregiver(s) eCOA. Parent(s)/caregiver(s) will complete the eCOA screening and twice daily for the entire duration of hospitalization, at approximately the same time each day. On the day of discharge, parent(s)/caregiver(s) will complete the eCOA before the subject leaves the hospital.
- i. The assessment on Day 1 must be recorded predose, before the LD. If the screening assessment was performed less than 8 hours prior to the LD, the predose assessment does not need to be performed.
- j. The first postdose assessment must be performed between 6 and 12 hours after the LD (on Day 1 or Day 2, depending on the time of LD).
- k. Clinical evaluation includes, but is not limited to, RSV disease symptoms, vital signs, oxygen requirement (type and duration), level of hospital care, duration of hospitalization, respiratory rate, body temperature, and SpO₂.
- l. SpO₂ will be assessed Q4h (± 30 minutes) while the subject is hospitalized through Day 7. In case the last SpO₂ assessment on Day 7 was performed after 8 PM, the first SpO₂ assessment on Day 8 should be performed within 8 hours from the last SpO₂ assessment on Day 7. For subjects who remain hospitalized after Day 7, SpO₂ assessment should then continue Q8h (± 1 hour) until 24 hours after the cessation of supplemental oxygen.
- m. A complete physical examination includes all body systems.
- n. A directed physical examination includes respiratory system, nose, ear, throat, facial and neck lymph nodes, and skin examination.
- o. A 12-lead ECG is strongly preferred but in cases where a 12-lead ECG is not possible or feasible, then a 6-lead ECG may be performed.
- p. An ECG needs to be recorded on Day 4 for subjects who remain hospitalized at this time. If discharged earlier than Day 4, the subjects need to have an ECG recorded on the day of discharge. The ECG will be performed 30 minutes to 3 hours after the first dose of that day.
- q. Leftover blood samples and nasal swabs may be used for exploratory biomarker analyses.
- r. The mid-turbinate nasal swab or endotracheal sample taken during screening is placed in 3 mL of transport media and split into several aliquots. Assessments for RSV diagnosis at screening will be performed by a local laboratory and confirmed by a central laboratory. Other assessments will be done by a central laboratory.
- s. Mid-turbinate nasal swabs (from the same nostril throughout the study) and/or endotracheal samples to assess RSV viral load and resistance should be taken by a trained study team member from Day 1 to Day 6 and on Day 7, Day 10, Day 14, and Day 28. Samples should be taken at approximately the same time each day prior to study drug administration. In case of nostril bleeding or irritation during the collection of a mid-turbinate nasal swab, all subsequent nasal swabs will be

performed on the contralateral nostril. Nasal swabs and endotracheal samples should be frozen as soon as possible after being collected. The actual times of sample collection and sample freezing must be recorded in the eCRF. Should the study drug duration be increased to up to 10 days (following review of the data by the IDMC), samples will be taken every day up to and including 1 day (+2 days) following the last dose of study drug. Quantitative culture of RSV using plaque assay may be performed centrally at timepoints selected by the virologist.

- t. Mid-turbinate nasal swabs and/or endotracheal sample must be taken as close as possible to and before the LD on Day 1.
- u. Only 1 blood sample will be collected if the biochemistry and hematology analyses are performed on the same day.
- v. A urinalysis can be performed during the screening period or on Day 1 prior to the LD dose. A sample will also be collected on the last day of dosing, within 3 hours of the last dose.
- w. At randomization, each subject will be randomly assigned to 1 of 2 PK sampling schemes, Group X or Y, with 3 PK timepoints per group: 2 samples will be taken on Days 1 to 2 and 1 random PK sample will be taken on Day 7. The actual dates and times of sample collection must be recorded in the eCRF. The IDMC may recommend that only 2 PK samples be used under the conditions of footnote w.
- x. The IDMC may recommend that only 2 PK samples (post Dose 1 and Day 7) be collected after at least 9 subjects have completed treatment with the 60 mg/kg LD/40 mg/kg MD lumicitabine regimen if the Option A design is chosen or after at least 9 subjects in each cohort have completed treatment with the highest active lumicitabine regimen available in their respective cohort if the Option B design is chosen. The post Dose 2 sample will not be collected in this scenario.

TIME AND EVENTS SCHEDULE: AFTER HOSPITAL DISCHARGE

Phase Day	Treatment Phase 3 to 6 ^b	Follow-up Phase ^a						
		7 ^c (+2 days)	8 to 9	10 (+2 days)	11 to 13	14 (+2 days)	15 to 27	28 (±2 days) EoS
Study Procedure								
Screening/Administrative								
Body weight		X		X		X		X
Body length and head circumference								X
Study Drug Administration ^d								
Dispense/administer study drug ^e and study medication log	X							
Clinical Efficacy Evaluations								
Parent(s)/caregiver(s) eCOA ^f	bid	bid	bid	bid	bid	bid	X	X
Clinical evaluation and clinician eCOA ^g		X		X		X		X
Oxygen saturation (SpO ₂)		X		X		X		X
Medical resource utilization and health economics assessment	X	X				X		X
Clinical Safety Evaluations								
Complete physical examination ^h								X
Directed physical examination ⁱ		X		X		X		
Electrocardiogram ^j								X
Vital signs		X		X		X		X
Nasal Swabs ^k								
Mid-turbinate nasal swab: RSV viral load, viral resistance (genome sequencing), biomarker, and infectious viral load (plaque assay) ^l	X	X		X		X		X
Clinical Laboratory Assessments								
Blood sampling for hematology ^m		X				X		
Blood sampling for biochemistry ^m		X				X		X
Urinalysis ⁿ		X				X		

Phase Day	Treatment Phase 3 to 6 ^b	Follow-up Phase ^a						
		7 ^c (+2 days)	8 to 9	10 (+2 days)	11 to 13	14 (+2 days)	15 to 27	28 (±2 days) EoS
Study Procedure								
Pharmacokinetics ^k								
Blood sampling for pharmacokinetics ^o : Group X or Group Y:		X						
Ongoing Subject Review								
Concomitant therapy	X	X	X	X	X	X	X	X
Adverse events	X	X	X	X	X	X	X	X

Abbreviations: bid: twice daily; ECG: electrocardiogram; eCOA: electronic clinical outcome assessment; eCRF: electronic case report form; EoS: end of study;

IDMC: Independent Data Monitoring Committee; MD: maintenance dose; PK: pharmacokinetic(s); RSV: respiratory syncytial virus; SpO₂: peripheral capillary oxygen saturation.

Footnotes:

- If a subject is discontinued from study drug, a follow-up visit will be scheduled 2 days (+2 days), 5 days (+2 days), 9 days (+2 days), and 23 days (±2 days) after the last dose of study drug was administered. Assessments should be performed as indicated in the Time and Events Schedule, respectively for the Day 7, Day 10, Day 14, and Day 28 visit.
- The subject may be discharged after Day 2 study procedures. Telephone calls to parent(s)/caregiver(s) to facilitate compliance with study procedures between outpatient study visits are encouraged at the discretion of the investigator. Should the treatment duration be increased, all assessments during that period will be performed at the same frequency as indicated in the Time and Events Schedule for Day 3 to Day 6; follow-up assessments are to be started 1 (+2) day after the last MD.
- If treatment duration is increased to up to 10 days, then all assessments performed on Day 7 will again be performed 1 day (+2 days) after administration of the last MD.
- MDs given twice daily. MDs may be extended to up to 19 doses over 10 days if recommended by the IDMC.
- Subjects will be dosed with MDs twice daily (minimum 8 hours and maximum 16 hours apart with no more than 2 doses per calendar day). Lumicitabine may be given without regard to food.
- An electronic device will be provided to the parent(s)/caregiver(s) the investigator/study-site personnel will provide sufficient information to enable the parent(s)/caregiver(s) to complete the parent(s)/caregiver(s) eCOA. Parent(s)/caregiver(s) will complete the eCOA twice daily (in the morning and in the evening) until the Day 14 visit, and once daily (in the evening) up to the Day 28 visit, at approximately the same time each day. Whenever possible, the same parent(s)/caregiver(s) should complete the eCOA throughout the study.
- Clinical evaluation includes, but is not limited to, RSV disease symptoms, vital signs, oxygen requirement (type and duration), level of hospital care, duration of hospitalization, respiratory rate, body temperature, and SpO₂.
- A complete physical examination includes all body systems.
- A directed physical examination includes respiratory system, nose, ear, throat, facial and neck lymph nodes, and skin examination.
- A 12-lead ECG is strongly preferred but in cases where a 12-lead ECG is not possible or feasible, then a 6-lead ECG may be performed.
- Leftover blood samples and nasal swabs may be used for exploratory biomarker analyses.
- Mid-turbinate nasal swabs (from the same nostril throughout the study) to assess RSV viral load and resistance should be taken by parent(s)/caregiver(s) from Day 3 to Day 6 and by a trained study team member on Day 7, Day 10, Day 14, and Day 28. Samples should be taken once daily at approximately the same time

each day prior to study drug administration. In case of nostril bleeding or irritation during the collection of a mid-turbinate nasal swab, all subsequent nasal swabs will be performed on the contralateral nostril. Should the study drug duration be increased to up to 10 days (following review of the data by the IDMC), samples will be taken every day at approximately the same time, up to and including 1 day (+2 days) following the last dose of study drug. The parent(s)/caregiver(s) should collect nasal swab specimens after being trained by the investigator/study-site personnel. The actual dates and times of nasal swab collection at home must be recorded in the eCOA by the parent(s)/caregiver(s). Nasal swabs collected at home should be stored immediately between 2°C and 8°C (in the refrigerator) and brought to the site at the next visit. Quantitative culture (plaque assay) will not be performed on samples collected at home but might be performed on samples collected at the hospital on Day 14 and/or Day 28 visit upon the request of the virologist.

- m. Only 1 blood sample will be collected if the biochemistry and hematology analyses are performed on the same day.
- n. A urinalysis will be performed on Day 7 if the subject is discharged before the sample on the last day of dosing can be collected.
- o. A random PK sample will be taken on Day 7. The actual dates and times of sample collection must be recorded in the eCRF.

ABBREVIATIONS

AE	adverse event
ALT	alanine aminotransferase
AUC	area under the plasma concentration-versus time curve
AUC _{0-24h}	area under the plasma concentration-versus time curve from time 0 to 24 hours after dosing
AUC _{0-last}	area under the plasma curve from time 0 to the time of the last quantifiable concentration
BCRP	breast cancer resistance protein
C _{12h}	predicted concentration at 12 hours post dose
C _{max}	maximum observed (or predicted) analyte concentration
CYP	cytochrome P450
DBP	diastolic blood pressure
DMID	Division of Microbiology and Infectious Diseases
DNA	deoxyribonucleic acid
EC ₉₀	90% of maximal effective concentration
ECG	electrocardiogram
eCOA	electronic clinical outcome assessment
eCRF	electronic case report form
eDC	electronic data capture
eGFR	estimated glomerular filtration rate
ER	emergency room
GCP	Good Clinical Practice
hMPV	human metapneumovirus
IB	Investigator's Brochure
ICF	informed consent form
ICH	International Conference on Harmonisation of Technical Requirements for Pharmaceuticals for Human Use
ICU	intensive care unit
IDMC	Independent Data Monitoring Committee
IEC	Independent Ethics Committee
IRB	Institutional Review Board
ITT	intent-to-treat
ITT-i	intent-to-treat infected
IV	intravenous
IWRS	interactive web response system
LD	loading dose
LRTI	lower respiratory tract infection
MAD	multiple ascending dose
MD	maintenance dose
NOAEL	no-observed-adverse-effect level
NOEL	no-observed-effect level
NTP	nucleoside triphosphate
OAT	organic anion transporter
OATP	organic anion-transporting polypeptide
PCR	polymerase chain reaction
PD	pharmacodynamic(s)
PK	pharmacokinetic(s)
popPK	population-derived pharmacokinetic(s)
PQC	product quality complaint
PRESORS	Pediatric RSV Electronic Severity and Outcome Rating System
qRT-PCR	quantitative real-time reverse transcriptase-polymerase chain reaction
QTcF	QT interval corrected for heart rate according to Fridericia's formula
RBC	red blood cell
RNA	ribonucleic acid
RSV	respiratory syncytial virus
SAE	serious adverse event
SAP	statistical analysis plan
SBP	systolic blood pressure

SD	standard deviation
SpO ₂	peripheral capillary oxygen saturation
SUSAR	suspected unexpected serious adverse reaction
t _{1/2}	half-life
ULN	upper limit of normal
WBC	white blood cell

DEFINITIONS OF TERMS

Electronic Clinical Outcome Assessment (eCOA)	Includes parent/caregiver-reported outcomes, clinician-reported outcomes, observer-reported outcomes and performance-reported outcomes collected on an electronic device.
---	---

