mitochondrial RNA polymerase. Further, JNJ-63549109 did not inhibit mitochondrial protein synthesis in either 8- or 28-day assays in the human hepatoma G2, human hepatoma type 7, and human T-cell leukemia derived MT-4 cell lines. In addition, JNJ-63549109 did not significantly inhibit the replication of a panel of viruses unrelated to RSV.

- Reduced progenitor differentiation and proliferation by JNJ-63549109 was seen for the human granulocyte-monocyte (50% inhibitory concentration = 8.71 μ M or 2,558 ng/mL) and erythroid precursor progenitors (50% inhibitory concentration = 9.21 μ M or 2,705 ng/mL) from bone marrow stem cells (14 days assay duration).

The major safety pharmacology findings were:

- No human ether-a-go-go gene potassium channel current blockage of lumicitabine or its metabolites.
- No central nervous system effects in rats up to 500 mg/kg/day.
- No cardiovascular and respiratory effects in dogs up to 500 mg/kg/day.

Toxicology Profile

Once administered, lumicitabine is rapidly and efficiently converted to JNJ-63549109. Thus, the toxicity profile of lumicitabine is primarily driven by JNJ-63549109.

The major toxicity findings were:

Repeat-dose Toxicity

- Target organ for toxicity was the hematopoietic system in adult and juvenile rats and dogs (JNJ-63549109 area under the plasma concentration versus time curve from time 0 to 24 hours after dosing [AUC_{0-24h}] $\geq 212,000$ ng.h/mL). The no-observed-adverse-effect level (NOAEL) doses of lumicitabine and exposure of JNJ-63549109 are presented in [Table 2](#).

Table 2: NOAEL Doses of Lumicitabine and Exposure of JNJ-63549109 in Adult and Juvenile Rats and Dogs After Repeated Dosing of Lumicitabine

Target Organ	Key Finding	Species/Age Group	Dose (mg/kg bid)	NOAEL (JNJ-63549109 AUC_{0-24h}) (ng.h/mL)
Hematology	↓ reticulocytes, ↓ red blood cell parameters, reversible	Juvenile rat (PND1-28) ^a	150	93,900 ^b
		Juvenile dog (PND7-34)	25	108,228
Bone marrow	Cytological changes in bone marrow cells, ↓ myeloid-to-erythroid ratios, reversible	Adult rat (14 days)	150	53,600
		Adult dog (14 days)	75	192,500

Abbreviations: AUC_{0-24h} : area under the plasma concentration versus time curve from time 0 to 24 hours after dosing; bid: twice daily; NOAEL: no-observed-adverse-effect level; PND: postnatal day.

- Effects in rats aged PND21-45 were similar to adult rats.
- Estimated on PND28 predose values.

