- The effect on reticulocytes was considered an early marker of toxicity, a monitorable parameter for humans. After 14 days of repeated dosing, these changes were reversible in both adult and juvenile animals.

- No effects on early developmental markers, neurobehaviour, respiratory function, bone geometry, bone densitometry, ophthalmological evaluations, or electrocardiograms (ECGs) in juvenile rats (150 mg/kg twice daily; JNJ-63549109 AUC_{0-24h} of 55,450 ng.h/mL) and dogs (75 mg/kg twice daily; JNJ-63549109 at AUC_{0-24h} of 258,862 ng.h/mL).

Genotoxicity

- Non-mutagenic (negative Ames test) and no DNA damage (COMET assay; 1,750 mg/kg/day for 3 days) potential for lumicitabine or its metabolites.
- Increases in structural chromosomal aberration in human peripheral blood lymphocytes induced by JNJ-63549109 (≥ 10 $\mu\text{g/mL}$). Positive micronucleus test in rats (≥ 425 mg/kg/day lumicitabine for 3 days) at high exposure of JNJ-63549109 (AUC_{0-24h} $\geq 107,983$ ng.h/mL). The NOEL for in vitro chromosomal aberrations was 5 $\mu\text{g/mL}$ and for in vivo micronucleus induction was an AUC_{0-24h} of 57,595 ng.h/mL.
- The mechanism of clastogenicity is an indirect, threshold-based mechanism of intracellular NTP pool disturbances rather than direct DNA reactivity, as described for other nucleoside analogs in the public domain.
- A maximum average threshold of JNJ-63549109 exposure in humans has been defined as an AUC_{0-24h} of 20,000 ng.h/mL (or 25,200 ng.h/mL in whole blood) ie, 2.7-fold lower than the NOAEL in the repeat-dose toxicity studies and well above the effective antiviral exposure in the human RSV challenge Study ALS-8176-502 (see Section [Clinical Studies](#) below).

Reproductive Toxicity

- The NOAEL for male reproductive toxicity/fertility was 250 mg/kg twice daily (JNJ-63549109 AUC_{0-24h} of 165,000 ng.h/mL). In view of the slight decrease in corpora lutea and corresponding decrease in implantations and viable embryos (without overall impact on female fertility or in utero survival), the NOEL for female reproductive toxicity as well as early embryonic toxicity was 250 mg/kg twice daily (JNJ-63549109 AUC_{0-24h} of 193,000 ng.h/mL).

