1.3.3. Known Risks

All therapies have the potential to cause adverse experiences. No formal adverse drug reaction determination has been performed.

In healthy adult subjects (N=234 dosed with lumicitabine), data from Phase 1/2a studies (ALS-8176-501, ALS-8176-502, ALS-8176-504, AL-8176-509, 64041575RSV1001/ALS-8176-511, and from 64041575RSV1003) indicate that lumicitabine was well tolerated with no safety concerns identified after receiving single doses up to 3,000 mg or multiple doses up to 750 mg twice daily on Day 1, followed by up to 500 mg twice daily MD for up to 13 days. In adult or pediatric subjects hospitalized with RSV, 3 hematological serious/severe AEs have occurred and subsequently resolved (see Section 1.3.4, Potential Risks).

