9.1.4. Posttreatment Phase (Follow-up)

Days 7 to 28

Subjects will be evaluated for a total of 28 days after randomization. If they are not hospitalized they will be required to return to the hospital for follow-up assessments as an outpatient on Day 7, Day 10, Day 14, and Day 28 as indicated in the [Time and Events Schedules](#). On Day 28 all subjects will complete the study either as an inpatient or outpatient.

Should the study drug duration be increased to up to 10 days (following review of the data by the IDMC, refer to Section [11.10](#), Independent Data Monitoring Committee), additional study drug may be provided if needed. If a subject is discontinued from study drug, a follow-up visit will be scheduled 2 days (+2 days), 5 days (+2 days), 9 days (+2 days), and 23 days (±2 days) after the last dose of study drug was administered. Assessments should be performed as indicated in the [Time and Events Schedules](#), respectively for the Day 7, Day 10, Day 14, and Day 28 visits.

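### Scheduled blood counts end at Day 14, although the marrow is the named target organ and blood is drawn again at Day 28 for biochemistry

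*Protocol*

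**What the plan says.** Hematology, in-hospital schedule: the row "Blood sampling for hematology ^u" is marked at screening, Day 2, Day 7 and Day 14. After discharge, "Blood sampling for hematology ^m" is marked at Days 7 and 14.

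Biochemistry: marked at screening, Day 7, Day 14 and Day 28 in hospital. After discharge, "Blood sampling for biochemistry ^m" is marked at Days 7, 14 and 28. A footnote to both schedules (u and m) says: "Only 1 blood sample will be collected if the biochemistry and hematology analyses are performed on the same day".

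Safety background: Protocol Section 1.1.2 states "Target organ for toxicity was the hematopoietic system in adult and juvenile rats and dogs", and adds "The effect on reticulocytes was considered an early marker of toxicity, a monitorable parameter for humans". Section 1.3.3 reports that in hospitalized RSV patients "3 hematological serious/severe AEs have occurred and subsequently resolved". Section 1.3.5 lists laboratory monitoring of hematologic parameters among the measures that reduce risk. Reticulocytes are in the hematology panel of Section 9.7.

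Extended dosing: the schedules allow up to 19 maintenance doses over 10 days on an IDMC recommendation. Section 11.10 lets this take effect without a protocol amendment. In that case the Day 7 assessments are repeated 1 day (+2 days) after the last maintenance dose.

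**The concern.** At Day 28 the child is bled for biochemistry but not for the panel that the drug's own safety profile points to. Section 16.1 says the laboratory tests were limited to those relevant to that profile, and the text available for this review gives no reason for leaving blood counts out of the last draw.

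At stake is the safety objective and what the IDMC can see of the main known risk. A fall in counts that begins after Day 14 and causes no symptoms would not be looked for. Recovery would not be documented by a scheduled late count in every child, as it would be for liver and kidney tests. Extended dosing makes this sharper: exposure doubles in length, but the last scheduled count may come sooner after the last dose. Because an extension needs no amendment, the monitoring schedule has to be right in advance.

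**Working it through.** **Inputs**
- Doses: 1 loading dose plus 9 maintenance doses (10 in all), or plus up to 19 (20 in all) if extended (schedule footnotes).
- Spacing: twice daily, at most 2 per calendar day (Section 6). Day 1 holds 1 or 2 doses, depending on when the loading dose is given.
- Visit windows: Day 14 (+2 days), Day 28 (±2 days).
- Repeat panel under extension: 1 to 3 days after the last dose.

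**Formulas**
- Last-dose day = 1 + (total doses − doses on Day 1) / 2, with the division rounded up.
- Gap = visit day − last-dose day.

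This assumes no missed doses and 2 doses on each full day.

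**The plan's own figures first.** With 10 doses, the last dose is on Day 1 + 8/2 = 5, or Day 1 + 9/2 (rounded up to 5) = 6. This matches the protocol's Day 5/6. Counted from Day 5, the Day 7, 10, 14 and 28 visits fall 2, 5, 9 and 23 days after the last dose. Those are the offsets in Section 9.1.4 for children who stop drug early: "a follow-up visit will be scheduled 2 days (+2 days), 5 days (+2 days), 9 days (+2 days), and 23 days".

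**Results**

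| Total doses | Doses on Day 1 | Last dose | Last dose to Day 14 count, nominal | With +2-day window | Repeat panel | Last dose to Day 28, nominal (with ±2 days) |
|---|---|---|---|---|---|---|
| 10 | 2 | Day 5 | 14 − 5 = 9 | 9 to 11 | none | 23 (21 to 25) |
| 10 | 1 | Day 6 | 14 − 6 = 8 | 8 to 10 | none | 22 (20 to 24) |
| 20 | 2 | Day 10 | 14 − 10 = 4 | 4 to 6 | Days 11 to 13 | 18 (16 to 20) |
| 20 | 1 | Day 11 | 14 − 11 = 3 | 3 to 5 | Days 12 to 14 | 17 (15 to 19) |

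The repeat panel is never later than Day 14, so it adds a count but does not extend hematology follow-up.

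**Consequence in the SAP.** SAP Section 2.1 ends the treatment phase 72 hours after the last intake. With a last dose on Day 11, that boundary falls on Day 14. The Day 14 count can then belong to the treatment phase, leaving the child with no scheduled follow-up-phase hematology for the tables of SAP Section 6.2.2.

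**Does Day 14 move under extension?** Four places bear on this:
- Footnote b of the after-discharge schedule starts follow-up assessments 1 (+2) day after the last maintenance dose, which can be read as restarting the follow-up calendar.
- Footnote c speaks of performing the Day 7 assessments again.
- Section 9.1.1 describes one additional clinic visit.
- Sections 3.1.1 and 9.1.4 keep the end of study at Day 28.

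The last three fit a Day 14 visit that stays put. Footnote b leaves doubt. On either reading, no hematology is scheduled at the final visit.

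**The case against.** The other side has several fair points, and most of them stand as limits on the finding.

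- **Known abnormalities are not dropped.** Section 9.8 requires laboratory changes to be followed until resolution. Section 9.7 does the same for clinically significant abnormalities that persist at the end of the study, and lets routine-care blood serve the study. Section 9.1.1 permits unscheduled samples. A reader might infer that anything after Day 14 is found only through symptoms, or that recovery of counts cannot be shown at all. Neither follows. The gap is confined to a new, silent change after a normal Day 14 count.
- **Early sampling has a rationale.** Hematology has a Day 2 sample that biochemistry lacks, reticulocytes are described as an early marker, and the animal changes were reversible. A reader might also infer that the target organ has the shortest laboratory follow-up of all. The schedules do not support that, because urinalysis also ends at Day 14.
- **Late onset is not shown.** Section 1.3.3 says the 3 human events resolved. It refers to Section 1.3.4 for detail, and the text available for this review does not show when they began or recovered.
- **Half-lives do not settle it.** A reader might express the gaps in terminal half-lives of about 63 hours. Section 1.1.2 gives that figure for healthy adults and adds that most plasma concentrations fell to low levels within 6 hours. It gives 17.6 hours in vitro and 29 hours in monkey lung for the active triphosphate. Nothing ties marrow effects to any of these values.
- **Re-timing the visits is not the remedy.** A reader might want the Day 14 and Day 28 assessments moved to the early stoppers' offsets. Nine (+2) days after a last dose on Day 10 or 11 is Days 19 to 22. SAP Section 2.1 assigns Day 21 onward to the Day 28 visit, and the secondary viral-load AUC still needs a Day 14 swab. The passages need reconciling; they do not support a new follow-up calendar.

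None of this supplies a scheduled late count or explains why the Day 28 draw omits one.

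**Conclusion.** The gap is real and modest. Scheduled hematology ends at Day 14 in both schedules, while the Day 28 draw covers biochemistry alone. The last scheduled count falls nominally 8 to 9 days after the last dose in the 5-day course, or 8 to 11 with the window.

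Under a 10-day extension it falls nominally 3 to 4 days after, or 3 to 6 with the window. That result is conditional on an IDMC recommendation, on all 20 doses being given as scheduled, and on Day 14 keeping its study day. The last of these is the better-supported reading but not the only one.

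The documents do not show that late cytopenia occurs. The case rests on the protocol's own choice of target organ and marker, and on how little a later count would cost. It is an inexpensive improvement in safety detection, not a flaw that undermines the trial.

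**What to change.** Add hematology, including reticulocytes, at Day 28 in both Time and Events Schedules, using the visit at which biochemistry is already drawn. The count would fall nominally 22 to 23 days after the last dose of the 5-day course, and 17 to 18 days after a 10-day course if Day 28 stays fixed. SAP Section 6.2.2 already summarizes each scheduled time point, and the SAP Day 28 window starts at Day 21, so no new SAP analysis is needed.

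The cost is one more local laboratory panel and a small extra blood volume. Footnotes m and u let one sample serve both panels, so no separate draw is needed. The total must stay within the 3 mL/kg limit of Section 16.1. Safety-sample volumes depend on local practice, so sites should confirm this for the smallest infants.

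Separately, reconcile footnotes b and c of the after-discharge schedule with the additional visit in Section 9.1.1 and the fixed Day 28 end of study. The protocol should then state unambiguously when safety follow-up, including hematology, takes place if dosing is extended. This is a wording change, best made before any extension is put into effect.
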